**Health care services, past year**

- Mental Health Emergency Service
- Outpatient visits for Schizophrenia (0-9, 10-29, 30-49, ≥50)
- Hospital admissions for psychiatric illness (1, 2, 3, ≥4)
- Psychotherapy
- Psychosocial Service contacts

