### Secondary

We will also investigate time to index treatment discontinuation, time to introduction of another psychotropic medication, psychiatric emergency department visits, all-cause hospitalization, and death.

We will investigate adverse effects of medications including incidence of major cardiovascular events and diabetes mellitus.

Outcomes	
Death	Date of death will be defined by the Social Security Death Master File.
Psychiatric Hospitalization	Hospital claims will define inpatient admissions with a first listed mental disorder diagnosis (ICD-9:290-310). High levels of agreement between diagnoses in inpatient medical records and inpatient claims have been reported for several mental disorder groups, including schizophrenia (100.0%), major mood disorders (98.7%), alcohol dependence (97.8%), and drug dependence (96.4%). 
Psychiatric ED Visits	Emergency department claims are a reliable source of diagnostic information in relation to medical records and a valid source of illness severity information.  Emergency department visits in which the first listed diagnosis is a mental disorder (ICD-9-CM: 290-319) will be defined as emergency department mental health visits.
Self-Injurious Behavior	Deliberate self-harm will be defined by an E-code of E950-E958, excluding late effects of deliberate self-harm (E959), on any inpatient, emergency department, or outpatient claim. High positive predictive values have been reported. 
Diabetes Mellitus	One or more claims with a physician diagnosis of diabetes will define diabetes mellitus. Using self-reported diabetes status as the criterion standard, $\geq 1$ physician claim with any diagnosis of diabetes or a diabetes complication (ICD-9 codes: 295.00-2950.93, 357.2, 362.0-362.02, 366.41) has acceptable sensitivity (68.5%) and specificity (96.9%), and (kappa=0.76).  Sensitivity of 90% and specificity of 93% with self-reported diabetes. 
Cardiovascular Events:	Acute myocardial infarction (AMI) (ICD-9-CM: 410) or stroke (430-438, except 435) will be defined by diagnostic codes on inpatient claims of $\geq 3$ days in duration.  With this AMI definition 75% met criteria for definite or probable AMI on independent review of cardiac biomarkers, electrocardiograms, presenting symptoms, and medical history, and an additional 12% had a suspected AMI. 

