## Approach to confounding

Physicians make treatment choices in light of available clinical information and as a result there is a risk of confounding by clinical indication for the treatments under study. Our design minimizes confounding by indication by focusing on diagnostic subgroups. To further reduce confounding, we will control for a broad range of potentially relevant factors from claims histories. These factors will be identified in the 365-day period before drug initiation and used to calculate propensity scores. In addition we will conduct sensitivity analyses to estimate the extent of unmeasured confounding necessary to fully explain our observed findings and we will conduct instrumental variable analyses if a suitable instrument is identified.

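### The propensity score counts only mental-health service use, which leaves avoidable residual confounding for all-cause hospitalization and death and possible differential detection of diabetes

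*Combined protocol and SAP*

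**What the plan says.** The section Approach to confounding promises that "we will control for a broad range of potentially relevant factors from claims histories", taken from the 365 days before drug initiation. Appendix 2 lists the variables. Under Health care services, past year, there are five: "Mental Health Emergency Service", "Outpatient visits for Schizophrenia (0-9, 10-29, 30-49, ≥50", "Hospital admissions for psychiatric illness (1, 2, 3, ≥4", psychotherapy, and "Psychosocial Service contacts". Elsewhere, Appendix 2 lists about 35 medical conditions coded in the past year and ten rows of non-psychiatric drug classes.

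The secondary outcomes include "psychiatric emergency department visits, all-cause hospitalization, and death". The adverse-effect outcomes are "incidence of major cardiovascular events and diabetes mellitus". For diabetes the case rule is: "One or more claims with a physician diagnosis of diabetes will define diabetes mellitus".

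**The concern.** The plan itself treats past service use as a confounder: Data source and cohort identification justifies the one-year look-back as time to collect such covariates. Psychiatric hospitalization and psychiatric emergency visits each have their own history in the score. The medical part of all-cause hospitalization has none, although the same claims hold it, and no reason is given.

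If prescribers choose between drug classes partly on medical frailty that the listed diagnoses and drugs do not capture, the weighted arms can still differ in prior medical admissions, and all-cause hospitalization and death would be confounded. If the arms differ in medical contact, more diabetes could be recorded in one arm at equal true risk. The planned check of standardized differences would not show either problem, because the variables are not on the list being checked.

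**Working it through.** The plan states no figure on this point, so there is none to reproduce. The check is an inventory, followed by an illustration of scale.

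**1. Inventory of Appendix 2.** Of the five service-use items, five are mental-health services and none is medical or all-cause. No other part of the appendix counts admissions, emergency visits or outpatient visits. (The psychiatric admission categories start at 1. Zero may be the unlisted reference level, and nothing here depends on it.)

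**2. Outcomes against baseline history.**

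| Outcome | Baseline history in the score | Missing |
|---|---|---|
| Psychiatric hospitalization (primary) | Prior psychiatric admissions | Nothing on this point |
| All-cause hospitalization | Prior psychiatric admissions; medical diagnoses and drugs | Count of non-psychiatric admissions |
| Death | Medical diagnoses and drugs | Any count of medical admissions or visits |
| Diabetes | Diabetes diagnosis, diabetic medication, other diagnoses and drugs | Amount of medical contact |

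For diabetes, the plan quotes claims sensitivities of 68.5% and 90%, so some true cases go unrecorded and detection depends on contact. The outcome is incidence. If patients with diabetes at baseline are left out of that analysis, the baseline diabetes diagnosis and diabetic medication will vary little among those at risk and cannot balance contact.

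**3. Scale of the confounding.** For an unadjusted binary confounder with prevalences p1 and p0 in the two arms and outcome risk ratio RR, the spurious ratio is [1 + p1(RR − 1)] / [1 + p0(RR − 1)]. All inputs are assumptions, and p1 and p0 are the values remaining after weighting.

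- RR 2.5, 20% vs 15%: (1 + 0.20 × 1.5) / (1 + 0.15 × 1.5) = 1.300 / 1.225 = 1.061.
- RR 2.5, 30% vs 20%: (1 + 0.30 × 1.5) / (1 + 0.20 × 1.5) = 1.45 / 1.30 = 1.115.
- Wider range: at 15% vs 10%, RR of 1.5, 2 and 3 give 1.02, 1.05 and 1.08. At 20% vs 10% they give 1.05, 1.09 and 1.17.

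**4. Where a spurious ratio of that size would show.** The number of first events at which the expected log-rank z equals 1.96 is D = 1.96² / [q(1 − q)(ln B)²]. Here B is the spurious ratio, read as a hazard ratio, and q is one arm's share of the episodes. The episodes come from Table 5, second antipsychotic vs antidepressant (vs mood stabilizer in mania).

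| Subgroup | Episodes | D at B = 1.061 | D at B = 1.115 |
|---|---|---|---|
| Uncomplicated | 27,005 + 25,061 = 52,066 | 4,358 (8% of episodes) | 1,290 (2%) |
| Schizoaffective | 6,393 + 9,692 = 16,085 | 4,543 (28%) | 1,345 (8%) |
| Depression | 2,192 + 4,646 = 6,838 | 4,995 (73%) | 1,479 (22%) |
| Mania | 1,580 + 2,107 = 3,687 | 4,442 (more than all episodes) | 1,316 (36%) |
| Anxiety | 611 + 1,110 = 1,721 | 4,751 (more than all episodes) | 1,407 (82%) |

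For example, in uncomplicated schizophrenia q = 27,005 / 52,066 = 0.519, so q(1 − q) = 0.2497. With ln 1.0612 = 0.0594, D = 3.8416 / (0.2497 × 0.00353) = 4,358. Weighting, and repeat episodes within patients, would raise these requirements.

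**The case against.** The strongest reply is that medical adjustment is already extensive. A coded diagnosis or a filled prescription requires contact with care, so about 35 conditions and ten drug rows are proxies for contact as well as measures of comorbidity. Several of the conditions are acute ones often treated in hospital, such as pneumonia, acute kidney failure, appendicitis and hip fracture. This stands as a reason to expect the bias to be smaller than the figures above. It does not close the gap, because as listed these variables do not separate one outpatient code from repeated admissions.

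A reader might infer that these outcomes are compared with no medical adjustment, or that all-cause hospitalization has no baseline value at all. Appendix 2 contradicts the first. The second is wrong in part, since all-cause admissions include psychiatric ones, whose prior count is in the score.

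A reader might also extend the point to cardiovascular events. The documents do not support that. Those events need an inpatient claim of at least three days, so outpatient contact does not drive detection, and the score includes many cardiovascular diagnoses and drug rows.

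That choice of class follows medical frailty is an assumption. The cohort is aged 18 to 64, and Appendix 1 excludes malignancy, epilepsy and some other serious conditions.

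The plan also includes an array analysis for unmeasured confounding, with BMI and diabetes as its example. That is a sound tool for factors absent from claims. Prior medical admissions are in the claims and can be adjusted for directly.

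Finally, diabetes detection depends on contact after initiation, which baseline visit counts only predict. That stands: for diabetes the remedy is partial.

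**Conclusion.** The gap is real and limited. It concerns secondary outcomes only: the non-psychiatric part of all-cause hospitalization, death, and the detection of diabetes. The primary outcome is not affected.

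The size is unknown. The range of about 1.06 to 1.12 assumes a 2.5-fold risk and imbalances of 5 to 10 percentage points that survive weighting (standardized differences of about 0.13 and 0.23), with no credit for the listed diagnoses and drugs.

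It would be wrong to infer that such a bias would appear as a significant difference throughout. At 1.06 the expected z could not reach 1.96 in mania or anxiety even if every episode had an event, and in depression 73% of episodes would need one. The risk is greatest in uncomplicated schizophrenia and schizoaffective disorder, where the sample size section itself notes that small differences become statistically significant.

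**What to change.** From the same 365-day look-back, derive three variables: number of non-psychiatric admissions (0, 1, 2, ≥3), number of non-psychiatric emergency visits, and number of medical outpatient visits. Add them to Appendix 2, to the propensity model and to the balance table, at least for all-cause hospitalization, death and diabetes. If they are left out, state why.

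The cost is three derived variables from claims already held and a slightly larger propensity model.

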### Subgroups

From the base study population described above, 5 clinical subgroups will be defined based on the presence of psychiatric diagnoses during the 30 days prior to and inclusive of the treatment change under study (index date) and who have this same diagnostic code from more than one provider to increase the validity of the diagnostic groups. The subgroups will be defined by codes to capture 1) uncomplicated schizophrenia (with schizophrenia codes from at least 2 different providers and without any diagnoses that would qualify them for the other subgroups during the 365 days prior to the index date), 2) schizoaffective disorder (ICD-9: 295.7) as the most recent schizophrenia-spectrum diagnosis, 3) depressive (ICD-9: 293.83, 296.2, 296.3, 296.9, 298.0, 300.4, 311), 4) manic (296.0, 296.4-296.8), and 5) anxiety (293.84, 300.00-300.02, 300.09, 300.20-300.23, 300.29, 300.3, 300.7, 308.0-308.9, 309.21, 309.81, 312.39, 313.0, 313.21, 313.23). These subgroups are defined to reflect the reason for the change in treatment.

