## Outcomes of interest

### Primary

The primary effectiveness outcome will be time to psychiatric hospitalization.

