## Follow-up and censoring

Follow-up will begin at the date of new treatment initiation (t0 or index date) and will end after 365 days regardless of changes in pharmacotherapy (intent-to-treat approach). We will also conduct secondary analyses using a 180-day follow-up period and an as-treated specification. In the as-treated approach, follow-up will end at discontinuation of the new treatment ( $>10$  days without drug) or addition of another psychotropic agent (antipsychotic, mood stabilizer, antidepressant, or benzodiazepine). All analyses will be censored at loss of Medicaid (because that is the data source) with one exception—in intent-to-treat mortality analyses, follow-up will not be censored at loss of Medicaid because date of death data comes from the Social Security Master File, not Medicaid.

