### *Propensity score estimation and application*

Propensity score methods involve two steps: estimation of the propensity scores and application of the propensity score. Estimation of the propensity scores involves decisions about which covariates to include in the prediction model of the propensity scores and what form the model should take. We will use expert opinion to select the variables to include in the propensity score. To estimate the propensity scores we will first use logistic regression including all baseline predictors occurring prior to treatment assignment. In addition, we will augment our analysis with another non-parametric method for building the propensity score model such as a generalized boosting algorithm implemented with regression trees. We will assess the sensitivity of our results to the choice of the propensity score model.

For the application of the propensity scores, we will use weighting by the odds to estimate the average treatment effect on the treated sample and weighting by the inverse probability of treatment weights to estimate the average treatment effect in the population.

We will examine the covariate balance using standardized differences in covariate means across the treatment groups after weighting, and address any significant imbalances.

**AIM 2 Heterogeneity of Treatment Effects:** Within the five subgroups, explore whether the comparative effectiveness and safety of alternative treatment strategies varies according to patient age and presence of a substance use disorder.

We will use similar Cox model techniques for the HTE analyses. First we will assess interaction of age and substance use variables with treatment. If such interactions are found, we will then perform analyses examining alternative treatment strategies stratified by age group or substance use.

The rationale for investigating patient age as a moderator of antipsychotic treatment effects follows from evidence that individuals early in the course of psychosis may respond differently to medications than people with more chronic illness. The rationale for investigating comorbid diagnosis of a substance use disorder as a moderator of treatment effects follows from evidence that people diagnosed with schizophrenia and comorbid substance use disorders respond more poorly to antipsychotic medications than those without comorbid substance use disorders.

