## Appendix 2: Variables included in the Propensity Score

### Demographics

---

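### The propensity score has past-year psychiatric admissions and emergency use but not how recent they were, so imbalance in recent discharge before t0 can go unadjusted and unseen

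*Combined protocol and SAP*

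**What the plan says.** The primary outcome is stated under Outcomes of interest: "The primary effectiveness outcome will be time to psychiatric hospitalization". Under Follow-up and censoring, "Follow-up will begin at the date of new treatment initiation (t0 or index date) and will end after 365 days".

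Confounders come from a single look-back. Approach to confounding says: "These factors will be identified in the 365-day period before drug initiation and used to calculate propensity scores". The list is headed "Appendix 2: Variables included in the Propensity Score", and its diagnoses, medications and services are all past-year terms. Under "Health care services, past year", psychiatric admissions are entered as "Hospital admissions for psychiatric illness (1, 2, 3, ≥4", and mental health emergency service has no date within the year. Propensity score estimation and application adds: "We will use expert opinion to select the variables to include in the propensity score". That section names no term for timing or recency, and checks balance by standardized differences in covariate means after weighting.

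The plan does use a short window before t0 elsewhere. Subgroups assigns patients by psychiatric diagnoses recorded "during the 30 days prior to and inclusive of the treatment change under study (index date", so as to reflect why treatment changed. That window dates a diagnosis, not an admission or discharge.

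**The concern.** Patients enter this cohort because treatment changed while symptoms persisted, emerged or recurred. A patient who left a psychiatric ward last week and one who left eleven months ago can both carry a count of one. Time since the last psychiatric admission is an obvious candidate predictor of the next, and the next admission is the primary outcome. It may also bear on which class is added, if some classes are chosen more often after an acute episode and others in routine outpatient care. If both links hold for a given pair of treatments, weighting on the yearly count leaves part of that confounding in place. The balance table would not reveal it, because a variable that is not in the table cannot be seen to be unbalanced.

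At stake is the reading of modest hazard ratios in the primary comparisons. Goal promises unbiased information, and Limitations relies on measured characteristics to keep residual confounding small. Recency is measurable from dated claims, so leaving it out is avoidable.

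**Working it through.** **Does any other part of the plan supply recency?**

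- *Eligibility.* Data source and cohort identification defines at least 90 days of stability by filled prescriptions alone, with active antipsychotic supply at t0. It is silent on admissions in those 90 days. The exclusion diagnoses in Appendix 1 do not remove recent discharges.
- *Subgroups.* The 30-day diagnosis may come from inpatient or outpatient care, so recently discharged patients and outpatients remain mixed within a subgroup.
- *Boosted propensity model.* It can fit the supplied covariates flexibly but cannot recover one that was not supplied.
- *Array analysis.* It asks how strong an unmeasured confounder would have to be; it does not adjust for this one.
- *Instrumental variable analysis.* It is conditional on finding an instrument.

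None of these adjusts for recency.

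**A yardstick from the plan.** Sample size gives at least 80% power for a 5.0-point difference in one-year admission with 1,534 patients per group in the depression subgroup (0.70 × 2,192 = 1,534.4). No base rate is stated. At an assumed 40% versus 45%, two-sided alpha 0.05, power is 80.0%; over base rates from 10% to 50% it runs from 79.1% to 98.7%. So the plan's figure reproduces to within a point. At 40%, five points is a risk ratio of 0.45/0.40 = 1.125 and a hazard ratio of ln(0.55)/ln(0.60) = 1.17. At 20% they are 0.25/0.20 = 1.25 and ln(0.75)/ln(0.80) = 1.29. The concern does not depend on these numbers; they give scale only.

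**Illustrative size of bias. All inputs are assumed.** Let p1 and p0 be the shares recently discharged in two arms after weighting, and h the hazard ratio for recent discharge. With no true treatment effect, the apparent ratio is

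B = [1 + p1(h − 1)] / [1 + p0(h − 1)].

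If the excess lasts only the first 90 of 365 days, with a flat baseline hazard and uncommon events, h is replaced by its time average, 1 + (h − 1) × 90/365.

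| p1 vs p0 | h | Excess lasts 365 days | Averaged h | Excess lasts 90 days |
|---|---|---|---|---|
| 20% vs 15% | 1.5 | 1.100/1.075 = 1.02 | 1.123 | 1.0247/1.0185 = 1.01 |
| 30% vs 15% | 2 | 1.30/1.15 = 1.13 | 1.247 | 1.0740/1.0370 = 1.04 |
| 30% vs 15% | 3 | 1.60/1.30 = 1.23 | 1.493 | 1.1479/1.0740 = 1.07 |

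Swapping the arms inverts the ratio (for example 1.30/1.60 = 0.81), so the direction is open. Against the hazard ratio of 1.17 at a 40% base rate, the whole-year figures for 30% versus 15% lie on either side of it, and the 90-day figures fall well short.

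**Would the 180-day analysis expose the problem?** Under the 90-day assumption the averaged h over 180 days is 1 + (h − 1) × 90/180, that is 1.5 for h = 2 and 2 for h = 3. With 30% versus 15%, B is 1.15/1.075 = 1.07 and 1.30/1.15 = 1.13. The shorter analysis would carry more of the bias, and a real early drug effect could produce the same pattern.

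**The case against.** The strongest reply is that the plan already narrows severity differences. Patients have had at least 90 days on one antipsychotic with no other psychotropic, those making more than one change at t0 are excluded, and comparisons are made within clinical subgroups. Emergency use, outpatient visit bands, psychotherapy, self-injury and past medication are in the score. Expert selection leaves room for a recency term, and Limitations acknowledges potential confounding. This is fair: these features may absorb part of the difference. None of them dates a discharge, and no recency term is listed.

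Three stronger readings are tempting, and the documents do not support them.

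- A reader might infer that two patients with equal admission counts receive the same propensity score. They receive the same value on one covariate; the scores coincide only if the other covariates also agree.
- A reader might infer that every primary comparison is biased. Confounding requires recency to differ between the two arms compared, and the documents show this for no pair. If a second antipsychotic (the usual reference) and a benzodiazepine were both favoured after acute episodes, their comparison might show little imbalance.
- A reader might infer that drugs begun in hospital are being counted as new starts at the first fill after discharge. The fill-based definition makes this possible, but the plan does not describe how inpatient drugs are recorded, so its frequency is unknown.

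The size is also open to challenge. A constant hazard ratio for a full year sits badly with an argument about near-term risk, so 1.13 to 1.23 leans high. A two-fold imbalance remaining after the yearly counts are balanced is itself an assumption.

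**Conclusion.** The gap is real and limited. The listed covariates do not separate otherwise similar patients by time since discharge, and the planned balance checks cannot detect an imbalance in it. Because recency plausibly predicts psychiatric hospitalization and may predict the class chosen, some comparisons may keep confounding that could have been removed. Neither its size nor its direction can be read from the documents.

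With 30% versus 15% recently discharged after weighting and a hazard ratio of 2 to 3, a true null would look like about 1.04 to 1.07 if the excess lasts 90 days, and 1.13 to 1.23 if it lasts the year; milder inputs give 1.01 to 1.02. The 90-day figures also assume a flat baseline hazard and uncommon events. The case for the change rests on its low cost and on the tie between covariate and outcome, not on any demonstrated bias.

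**What to change.** Add two terms to the propensity score list in Appendix 2:

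1. Time from last psychiatric discharge to t0, in categories, for example none in the past year, 0–30, 31–90 and 91–365 days, collapsed where cells are small.
2. An indicator for a mental health emergency visit in the 30 days before t0.

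Report the standardized differences for both after weighting, alongside the other covariates. As a supporting sensitivity analysis only, exclude or stratify episodes whose t0 falls within 30 days of a psychiatric discharge. State that exclusion changes the population, since it removes some of the acutely symptomatic patients the study is about.

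The cost is a few derived variables from inpatient and emergency claims already used for Appendix 2, and one further analysis run. No new data are needed. Weights may become somewhat more variable if recency strongly predicts treatment, mainly in the small groups: in Table 5, anxiety with a second antipsychotic has 611 episodes and mania with a benzodiazepine has 840. Collapsing categories there limits this.
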